Individuals who express interest in the study will be screened for eligibility by the study coordinator or a research assistant via phone. A phone script will be used that is IRB-approved. If they meet criteria, the participant will be asked to complete study scales online via RedCap, a secure

online data capture system. These self-report scales will include the ADHD Rating Scale (ADHD-RS), Adult Self-Report Form (ASR), BRIEF-A, Epworth Sleepiness Scale (ESS), and the Pittsburgh Sleep Quality Index (PSQI). If a subject completed any of these scales for another study in our department or through the adult ADHD clinical program within the past year prior to screening they may not have to repeat the scale(s) for the current study unless asked to do so by a study staff member based upon clinician judgment. However, in the case where scales completed previously will be reviewed, verbal permission will be obtained from the participant that it is okay to review these previously completed scales to assess inclusion and exclusion criteria.

Subjects who have participated in research in our program may be eligible to participate in this study. Other medical records on a subject will not be used at any point, unless explicit written permission is provided by the subject.

Many subjects referred to this study will first participate in our general screening protocol entitled, "Screening Protocol for Adults with Attention Deficit Hyperactivity Disorder" (Protocol # 2002-P-001856). Under this protocol, advertisements from our research group include a link that allows individuals to contact us by email, phone, or via a URL link to a REDCap form. After participating in this screening protocol, subjects are referred to specific studies based upon eligibility requirements (i.e. age, prior medication efficacy or tolerability).

Study Entry Criteria

Inclusion Criteria:

- 1. Adults ages 18-65 years of age.
- A diagnosis of childhood-onset ADHD, meeting the DSM-V criteria for ADHD in adulthood, including at least 5 current symptoms of inattentive or impulsive-hyperactive traits, and childhood onset by age 12, defined as two symptoms of inattentive or of impulsive/hyperactive traits by the age of 12.
- 3. A score of 20 or more on the Adult ADHD Investigator Symptom Report Scale (AISRS)

Exclusions

- 1. Individuals with known renal insufficiency or renal impairment.
- 2. A history of intolerance to solriamfetol

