- 3. Pregnant or nursing females, and individuals unwilling to use adequate contraceptive methods to avoid conception while they are receiving study agent and for 1 month after the last dose of study agent. For female subjects of childbearing potential adequate contraceptive methods will include: a medically acceptable form of birth control (such as male or female condoms with or without spermicidal agent, diaphragm or cervical cap with spermicide, medically prescribed IUD, hormonal contraceptives like birth control pills, or abstinence). For male subjects this will include use of male condom, being status post vasectomy at least 4 months prior to initiation of study drug exposure, or abstinence during the study.
- 4. A known unstable major medical illness including hepatic, renal, gastroenterological, respiratory, cardiovascular (including hypertension ≥ 140/90 mmHg), endocrinologic (e.g. thyroid), neurologic (e.g. seizure), immunologic, hematologic, or psychiatric (including an active substance use disorder, psychosis, bipolar disorder, major depression) disorder.

- 5. Any medical condition that the Principal Investigator (PI) believes will be exacerbated by study participation.
- 6. A history of cancer (except localized skin cancer without metastases or in situ cervical cancer) within 5 years prior to screening.
- 7. A known history of narrow-angle glaucoma.
- 8. Current (within 3 months) DSM-V criteria for abuse or dependence with any psychoactive substance other than nicotine.
- 9. Multiple adverse drug reactions, defined as previous moderate to severe adverse experiences while on two or more chemically unrelated compounds, where these reactions were unpredictable from the known pharmacology of the drug.
- 10. Any other concomitant medication with primarily central nervous system activity that are catecholaminergic such as stimulants or atomoxetine, or have strong noradrenergic mechanisms of action such as duloxetine or venlafaxine or buproprion. Subjects may be included who are taking stable doses of agents with primary serotonergic (such as selective serotonin reuptake inhibitors or buspirone), gabaergic (such as gabapentin, pregabalin), or other anticonvulsants. We will also allow participation by individuals with rare (predicted to be less than twice a week) use of prn benzodiazepines or sedative-hypnotics.
- 11. Current use of MAO Inhibitor or use within the past two weeks.

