Virtual or written informed consent will be obtained via Adobe esign or courier mail service after subjects are screened for potential participation, prior to the performance of other protocol procedures, and prior to administration of study drug. Screening of participants will involve use of a survey, which may be reviewed in person or via televisit or telephone. We also may post all or part of this form on REDCap, for participants to complete at their convenience if they prefer. During screening, we will collect minimum identifying information that allows communication or re-contacting, such as first name or telephone number. The information collected from this phone survey will be reviewed by study staff, and if they appear likely to meet criteria for safe inclusion in the study, the participant will be asked to schedule for an evaluation visit. As part of this evaluation, they will complete study scales online via RedCap, a secure online data capture system.

Informed consent will be obtained by a licensed study clinician or study staff. The study, risks and benefits will be explained in simple terms, and any questions from participants will be answered. Participants will be given as much time as they feel is necessary to make a decision regarding their consent. Subjects will be informed that participation is entirely voluntary, and they may withdraw consent at any time without penalty.

After providing study information and obtaining IRB approved informed consent, participants will undergo a comprehensive assessment including a psychiatric assessment with a clinician reviewing current and lifetime DSM-V Axis I conditions, medical history including history of any cardiac symptoms or abnormalities reported on routine clinical exams, and eligibility per inclusion and exclusion criteria. This assessment will also include staff-review of forms filled out online by study participants in REDCap. The information obtained at this visit will be reviewed to assure that all inclusion and exclusion criteria are met prior to receiving study agent at the baseline visit. Subjects who do not meet all the criteria for enrollment after these assessments will be discontinued.

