We anticipate that a small minority of subjects may enter this trial following completion of withdrawal from other protocols in our office, and that there may be procedural overlap. So as to not burden subjects with redundant time commitments, we will use the following *diagnostic* data previously collected: If a subject has completed an equivalent evaluation with one of the study clinicians within the previous year prior to entrance into this study, they will not be asked to repeat any overlapping diagnostic procedures. With subjects' permission, we will use the diagnostic data that had been previously collected, and document this data and when it was collected in our substantiation of how the individual meets diagnostic criteria in the evaluation documentation for the current study. However, the study clinician will review the interval time period to assess for clinically significant medical or psychiatric history, to ensure that the subject meets all study entrance criteria.

Safety Assessments:

Vital signs (blood pressure, pulse) will be monitored at each visit during the study. If there is suspicion that the participant's eligibility to participate has changed (e.g., evidence they have taken an illicit drug), he/she will have a discussion with the doctor to determine if he/she can be in the study. It will be up to the principal investigator's judgement to determine if the subject continues to meet study inclusion and exclusion criteria. For example, subjects will be discontinued if there is suspicion of ongoing substance abuse by history or by confirmation of ongoing abuse by positive drug test, or evidence of inability to adhere to study procedures (e.g. missing two visits in a row, or otherwise insufficient participation to monitor safety in the judgement of the investigators). Drug testing will not

be done systematically but will be available to clinical investigators to determine participant eligibility and safety before and throughout study participation. Participants will be told at the time of consent that random drug screening may occur at the choice of study investigators.

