We will also report whether there is a difference in change in baseline to endpoint sleepiness and changes in sleep quality during the study.

Data processing and management will follow procedures developed by the investigators and used in ongoing studies.

VII. RISKS AND DISCOMFORTS

All efforts are made to minimize risks to subjects. Consistent with good clinical practice, safety will be monitored by the Principal Investigator, and will reflect the oversight of co-investigator study clinicians. Adverse events will be recorded and reported according to institutional policies. Risks of the study agent have been considered in developing the exclusionary criteria for this proposal.

Study clinician evaluation and subject questionnaires:

Some questions may make subjects feel uncomfortable. Subjects may refuse to answer any question they wish. In the event that a participant reports risk of harm to himself or herself, or to another person, study clinicians will assess the level of risk, and take appropriate actions, including disposition of an immediate referral to a local Psychiatric Emergency Room.

Risks of Study Agent – Solriamfetol:

Solriamfetol is approved by the US Food and Drug Administration to improve wakefulness in adult patients with excessive daytime sleepiness associated with narcolepsy or obstructive sleep apnea (OSA).

FDA indications for Solriamfetol include recommendation for starting at 75 mg in patients with daytime fatigue in narcolepsy, and titration from 75 mg to 150 mg after three days. Our protocol titrates more conservatively, following the weekly pattern of dose increase that is more typical of clinical trials in ADHD. While this interval for increase was chosen primarily to give subjects longer to evaluate ADHD symptom experiences, and to mimic pattern of study assessments in other ADHD trials, it will also give greater time for subjects to evaluate adverse effects before increasing them with a dose increase.

We chose not to exceed 150 mg in this study in keeping with FDA approved dosing for individuals with excessive daytime sleepiness. The package label notes that heart rate and blood pressure changes appear to be dose-dependent in populations studied, such that doses above 150 mg could be expected to add more risk. The label advises to avoid patients with known cardiovascular and cerebrovascular disease, preexisting hypertension, and patients with advanced age, advice we follow in this protocol.

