Vital Signs (BP, pulse)		X*	х	х	х	х	х	x
Clinician Evaluation	x							
AISRS	х	х	х	х	х	х	х	х
ADHD-RS	X*							х
CGI ratings		х	х	х	х	х	х	х
GAF		х	х	х	х	х	х	х
Adverse Events		x	х	х	х	x	x	х
Concomitant Medications		х	х	х	х	х	х	x
BRIEF-A		X*						х
ASR	X*							
ESS		X*						х
PSQI		X*						х
Pill counting				х		х		х
Pregnancy test	х							х

^{*} Can be completed at either evaluation or baseline visit as long as those visits are within 10 days

^{**}If a subject terminates participation early, all assessments at week 6 will be made at study completion.

IX. Monitoring and Quality Assurance

The Principal Investigator will meet regularly with study staff to address procedural issues and the study coordinator will audit each subject's data within 48 hours of each study visit. Furthermore, all data will be audited by the study statistician with the assistance of the database manager on a regular basis to ensure the progress of the study and confirm that all necessary data is being collected and can be transitioned to the statistical package smoothly. Co-investigators are actively involved in the monitoring and quality assurance of these trials. Periodic quality assurance audits will ensure accuracy and completeness of all subject documents, IRB files and correspondence, and the informed consent documentation.

XI. Telehealth Remote study procedures

Subjects will be offered the option to participate via remote telehealth. Individuals may choose a mixture of in-person and telehealth visits, or just one or the other, as suits scheduling convenience or prudent safety practice. For example, during a public health infectious disease crisis such as the COVID-19 pandemic, risks to participants may be reduced by remote televisits. We will not conduct in-person visits unless approved by Partners healthcare and Massachusetts General Hospital.

Recent Virtual Visit Clinical Growth for COVID-19

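### The risk section says the protocol avoids known cardiovascular and cerebrovascular disease and preexisting hypertension, but the entry criteria leave stable heart disease, past stroke and treated hypertension to the principal investigator's judgement

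*Combined protocol and SAP*

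**What the plan says.** Section VII (Risks of Study Agent) explains the 150 mg ceiling, notes that heart rate and blood pressure effects appear to rise with dose, and says the label advises to "avoid patients with known cardiovascular and cerebrovascular disease, preexisting hypertension, and patients with advanced age, advice we follow in this protocol". The closing clause is a statement about this protocol, not only about the label.

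The criteria meant to carry it out are in section III:

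- Inclusion 1: "Adults ages 18-65 years of age".
- Exclusion 4: "A known unstable major medical illness including hepatic, renal, gastroenterological, respiratory, cardiovascular (including hypertension ≥ 140/90 mmHg"). The list goes on to neurologic illness, with seizure as the example, under the same opening qualifier.
- Exclusion 5: "Any medical condition that the Principal Investigator (PI) believes will be exacerbated by study participation".

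Section V describes how these are applied. The evaluation includes a "medical history including history of any cardiac symptoms or abnormalities reported on routine clinical exams", and the information is reviewed to assure that "all inclusion and exclusion criteria are met prior to receiving study agent at the baseline visit". The same section records concurrent medications at screening (Assessments and Instruments) and takes a past and present treatment history (Concomitant Medications / Treatments). On blood pressure, Safety Assessments states: "Vital signs (blood pressure, pulse) will be monitored at each visit during the study". The timeline's footnote to the first reading is: "Can be completed at either evaluation or baseline visit as long as those visits are within 10 days".

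**The concern.** The risk section describes its groups by *known* disease and *preexisting* hypertension. Exclusion 4 works by *unstable* disease and a pressure threshold. The first description is wider, and the difference is made up of identifiable patients: someone with stable coronary disease, someone with a stroke some years ago, and someone whose hypertension is controlled on treatment.

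What is at stake is participant safety and the accuracy of a stated safeguard. The drug has cardiovascular effects that the protocol itself describes as apparently dose-dependent, and dosing is a forced titration from 75 mg to 150 mg as tolerated. A reader weighing the risk would take section VII to mean that these patients are kept out. Under the criteria as written, some of them can be enrolled and dosed with no deviation to report.

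**Working it through.** No arithmetic beyond a count applies. The check sets the four groups named in section VII against the inclusion criteria and the 16 numbered exclusions in section III.

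| Group named in section VII | Objective rule in section III | What the rule leaves open |
|---|---|---|
| Advanced age | Inclusion 1, upper limit 65 | Nothing |
| Known cardiovascular disease | Exclusion 4, if unstable | Known but stable heart disease |
| Preexisting hypertension | Exclusion 4, at 140/90 mmHg or more | Diagnosed hypertension treated to below 140/90 |
| Known cerebrovascular disease | None by name; an unstable case could fall under the cardiovascular or neurologic items of exclusion 4 | Past stroke or TIA, now stable |

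Count: 1 covered + 2 partly covered + 1 not named = 4.

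**Do other exclusions close the gaps?** None of the 16 names stroke, TIA, cerebrovascular disease or treated hypertension. The medication exclusions (10 to 12) concern centrally acting catecholaminergic agents, MAO inhibitors and dopaminergic or sympathomimetic drugs; they do not name antihypertensives. Exclusion 16 could catch a stroke survivor whose symptoms obscure the ADHD diagnosis, but that is a judgement about diagnosis, not about cardiovascular risk. That leaves exclusion 5.

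**How does exclusion 5 work?** It is a listed exclusion. Once the principal investigator believes a condition will be exacerbated, the subject is ineligible, and section V says that subjects who do not meet the criteria are discontinued. The discretion lies in forming the belief. A positive history of heart disease, stroke or hypertension does not itself trigger anything.

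**Would the conditions be known in time?** Largely yes. Medical and cardiac history, concurrent medications and treatment history are all taken before dosing. A reading below 140/90 would not reveal treated hypertension, but the medication list and history should. What is missing is an automatic consequence of what screening finds.

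**Can the pressure limit be applied before dosing?** Yes. The first reading is taken at evaluation or baseline, and all criteria must be met before study agent is given.

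**What does the label text quoted in section VII say?** Later in the same subsection, the quoted label language asks for hypertension to be controlled and for the drug to be avoided in unstable cardiovascular disease, serious arrhythmia and other serious cardiac conditions. Exclusion 4 is close to that text, although no criterion names arrhythmia or other serious heart problems. The clear mismatch is therefore between the sentence claiming that the advice is followed and exclusion 4.

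**The case against.** The best case on the other side is that this is a loose paraphrase in a risk narrative, not a faulty criterion. The quoted label text allows controlled hypertension, exclusion 4 largely tracks it, and correcting one sentence would remove the inconsistency. Exclusion 5 is binding once invoked, and the investigator applies it under a protocol that says it follows the advice. Screening would bring the relevant history to light, and subjects have several protections once enrolled.

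Much of this stands. It fixes how far the point goes, and four stronger readings that a reader might infer are not supported:

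- *That these patients enter unchecked.* They do not; exclusion 5 applies and is mandatory once the judgement is made.
- *That treated hypertension would go unnoticed.* The medication and treatment histories make that unlikely.
- *That the protocol departs from the label.* The label itself is not in the documents, and the part quoted is narrower than the paraphrase.
- *That the protocol reports sudden death, stroke or heart attack with solriamfetol.* The sentence on those events concerns stimulants. The protocol uses sympathomimetic ADHD agents as a risk comparison and does not attribute the events to the study drug.

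What does not stand is the conclusion that the matter is only editorial. Rewording section VII would make the text consistent but would not change who is exposed. A rule that matches the stated safeguard would change it, at little cost. Nor does the paraphrase argument help with stroke: no criterion names it, so even a reader who accepts exclusion 4 for heart disease finds no explicit provision for it.

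**Conclusion.** The point holds. Section VII states that four groups are avoided; the criteria give an objective rule for one in full and two in part, and do not name the fourth. Stable known heart disease, past stroke or TIA, and hypertension treated to below 140/90 mmHg depend on the principal investigator's judgement under exclusion 5.

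This rests on reading *unstable* in exclusion 4 as qualifying the whole list that follows, which is the plain sense of the sentence. The protocol does not define the term, so even that rule involves some judgement.

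The size cannot be put as a number of subjects, because the documents give no prevalence for these conditions. The ceiling is small: up to 30 of the 60 subjects receive solriamfetol, for six weeks. Risk is further limited by blood pressure and pulse at every visit, the 150 mg cap, return to 75 mg if 150 mg is not tolerated, and discontinuation for intolerable or clinically relevant serious adverse events. The practical risk is modest, but the change should still be made. A reader might infer that the treatment comparison is compromised; nothing here bears on the efficacy analysis.

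**What to change.** Add one exclusion in section III, with a matching line on the screening form, along these lines: *known cardiovascular disease, including serious arrhythmia or another serious cardiac condition; known cerebrovascular disease, including past stroke or TIA; or diagnosed hypertension, whether or not treated.* Keep the 140/90 mmHg limit in exclusion 4 for raised pressure without a diagnosis, and keep exclusion 5 for what no list foresees. The new criterion can be checked at the evaluation visit from information already collected.

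If the investigators mean to admit controlled hypertension, as the quoted label text allows, keep the heart disease and stroke exclusions and narrow section VII to say that hypertension is excluded at 140/90 mmHg or more and that treated hypertension below that is admitted subject to exclusion 5. Rewording section VII without adding any exclusion would restore consistency but leave exposure as it is.

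The cost is a few more screen failures and a slightly narrower population. Because enrolment continues until 60 subjects have consented and been exposed to study agent or placebo, the screen failures would lengthen recruitment rather than reduce the sample.
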